Endpoint	Main	Sensitivity
Primary: Change from baseline MADRS total score	MMRM (observed cases [OC], FAS)	MMRM (MI, complete cases, and treatment compliant cases, FAS)

Secondary: ≥50% improvement in MADRS total score	Logistic Regression (OC, FAS)	Logistic Regression (MI, complete cases and treatment compliant cases, FAS)
MADRS total score ≤ 10	Logistic Regression (OC, FAS)	Logistic Regression (MI, complete cases and treatment compliant cases, FAS)
Change from baseline in QIDS-SR-16, GAD-7 and EQ-5D-3L	MMRM (OC, FAS)	MMRM (complete cases and treatment compliant cases, FAS)
CGI-S, CGI-I score	MMRM (OC, FAS)	MMRM (complete cases and treatment compliant case, FAS)

K. Exploratory Analyses

All descriptive statistics analyses which are performed on the FAS as detailed in [Section VII Efficacy Analyses](#) for the primary and secondary endpoints will be repeated based on the subgroup categories as detailed in [Section V.H Subgroups of Analysis Populations](#).

L. Pharmacokinetics

Not applicable.

VIII. Safety Analyses

All safety related analyses will be performed on the SAS except for the listings of SAEs and AEs leading to death, which will be presented for the FAS.

A. Treatment Exposure and Compliance

Study treatment non-compliance is defined as having an infusion duration with a deviation of more than 5 minutes from the 40 minute infusion time (ie, <35 or >45 minutes of infusion duration).

Exposure to PCN-101 or Placebo will be summarized with descriptive statistics for the following exposure measures.

1. Duration of Treatment (minutes)

- If not interrupted, defined as the time of end of infusion – the time of start of infusion+1
- If interrupted, defined as the (time of end of infusion – the time of start of infusion+1) - (infusion restart time – infusion stop time+1)

Details of the infusion drug administration will be listed by subject.

B. Adverse Events

Adverse events (AEs) will be documented on the AE eCRF and monitored continuously throughout the study. Adverse events will be coded using the Medical Dictionary for Regulatory Activities (MedDRA), version 23.0 or higher, associating lower-level terms with preferred terms and system organ classes by the primary hierarchy. All adverse events will be included in the listings.

Treatment-emergent AEs (TEAEs) are defined as AEs that first occurred or worsened in severity after the start of infusion but no later than the second follow-up visit.

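### The exposure formula in SAP Section VIII.A adds a minute to uninterrupted infusions but not to infusions paused once, and may shift the compliance window for the former

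*SAP*

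**What the plan says.** SAP Section VIII.A (Treatment Exposure and Compliance) contains two rules.

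- **Compliance.** Non-compliance is "having an infusion duration with a deviation of more than 5 minutes from the 40 minute infusion time", which the SAP spells out as "<35 or >45 minutes of infusion duration".
- **Exposure.** Duration of Treatment, in minutes, is to be summarized descriptively. Without a pause the rule is "If not interrupted, defined as the time of end of infusion", then a minus sign and "the time of start of infusion+1". With a pause, the same expression is reduced by a bracket reading "infusion restart time – infusion stop time+1".

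The protocol counts the 40 minutes as elapsed time from the start of the infusion (Section 1.3, footnote b, and Section 8.0).

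Compliance status selects subjects for a sensitivity analysis of the primary endpoint (SAP Section VII.G). Table 3 in SAP Section VII.J also lists treatment-compliant analyses for response, remission, QIDS-SR-16, GAD-7, EQ-5D-3L, CGI-S and CGI-I.

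**The concern.** Adding 1 is right when counting calendar days with both ends included. It is not right for the time between two clock readings, which is simply the later reading minus the earlier one. As written, an infusion given exactly to plan appears in the exposure table as 41 minutes.

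The formula is also inconsistent with itself. The interrupted version adds 1 to the total and subtracts it again with the gap, so the extra minute vanishes. No single counting convention gives both results, so even a reader who accepts the plus 1 as a house rule is left with two scales in one table.

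Two things are at stake: the accuracy of the exposure summary and, if the same variable drives the compliance rule, the membership of the treatment-compliant subset at its edges.

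**Working it through.** **Inputs.** Nominal infusion time 40 minutes, tolerance 5 minutes, and the two duration formulas (all SAP Section VIII.A). The end-of-infusion window of ±2 minutes is from protocol Section 8.0. Write S and E for start and end, P and R for pause and restart, d = E − S for elapsed time, and D for the SAP's duration.

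**The plan's own limits.** 40 − 5 = 35 and 40 + 5 = 45. The stated limits reproduce, and the compliant range is 35 to 45 inclusive.

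**Uninterrupted.** D = d + 1.
- d = 40 gives D = 41. The excess is 1 minute, and 1/40 = 2.5%.
- If compliance is judged on D, 35 ≤ d + 1 ≤ 45 gives 34 ≤ d ≤ 44. The symmetric 40 ± 5 becomes −6/+4 in elapsed minutes.

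**Interrupted once.** D = (E − S + 1) − (R − P + 1) = (E − S) − (R − P), the net infusion time.
- Example with a 5-minute gap and 40 net minutes: E − S = 45, so D = 46 − 6 = 40.
- The window for net time stays at 35 to 45 for any gap length.

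**Same infusion time, two results** (if the rule uses D):

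| Net minutes | D, no pause | Class | D, one pause | Class |
|---|---|---|---|---|
| 34 | 35 | compliant | 34 | non-compliant |
| 40 | 41 | compliant | 40 | compliant |
| 45 | 46 | non-compliant | 45 | compliant |

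Over whole-minute elapsed times from 30 to 50, the values 34 and 45 are the only uninterrupted ones whose class differs from that under plain elapsed time. With finer recording, the affected bands would be 34 up to but not including 35, and above 44 up to 45.

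**Infusions that end on time.** Elapsed times of 38 to 42 minutes (40 ± 2) give D = 39 to 43, inside 35 to 45. None is reclassified.

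**More than one pause.** The formula is written for a single gap. If each further gap were subtracted with its own plus 1, D would equal net time − 1 with two gaps (window 36 to 46) and net time − 2 with three (window 37 to 47).

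**With the plus 1 terms removed.** D is the net infusion time in every case, 40 is reported as 40, and the window is 35 to 45 with or without pauses.

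**The case against.** The strongest objection is that the SAP never links the two rules. The compliance sentence speaks of infusion duration. The formula follows under the exposure summary and defines an item with a different name. If the programmer judges compliance on plain elapsed time, the window stays at 35 to 45 and only a descriptive table is affected. This stands, and the 34 to 44 window must be stated conditionally. The link is nevertheless the natural reading, because this is the only duration the SAP defines and it sits in the same section.

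Second, the practical effect is very small. Infusions run on an electronic pump, those ending within the protocol's ±2 minutes keep their class, and the values that do change lie 5 or 6 minutes from nominal. This also stands. The documents give no basis for an expected number of affected subjects.

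Third, the recording resolution is not given, so a 40-minute difference between whole-minute readings is itself uncertain. That does not rescue the formula. If both readings are truncated to the minute, the true elapsed time lies within a minute either side of the difference. The plain difference is then the central value, and adding 1 gives the upper extreme.

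Fourth, the plus 1 could be read as attached to the start time, end minus (start + 1). That would report 39 for a 40-minute infusion and give a window of 36 to 46. It is a less ordinary reading and no more correct.

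Fifth, the protocol's own definition of noncompliance (Section 6.4) differs from the SAP's. It has no 5-minute tolerance and includes receiving less than the full infusion. This is a separate conflict that could move more subjects than a one-minute offset, and correcting the formula does not settle it.

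**Conclusion.** The exposure formula is wrong as written. It overstates every uninterrupted infusion by 1 minute and is inconsistent with its own treatment of an infusion paused once. That conclusion needs only the ordinary left-to-right reading and the protocol's counting of the 40 minutes as elapsed time.

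The shift of the window to 34 to 44 minutes rests on a further assumption, that the compliance rule uses this derived duration. It applies to uninterrupted infusions only; those paused once keep 35 to 45.

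A reader might infer that the SAP in effect sets a 34 to 44 minute rule for everyone, or that the efficacy result is at risk. The documents support neither. The SAP states 35 to 45 and does not tie that rule to the formula. The primary analysis is run on the FAS with all observed values kept under a treatment policy (SAP Sections VII.A and VII.F), so compliance status does not enter it. What can change is the exposure summary and, at the boundary values, membership of the treatment-compliant sensitivity analyses. With 31 subjects planned per arm, one such change would be 1/31, about 3% of an arm. This is a minor correction, worth making because it is free.

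**What to change.** In SAP Section VIII.A:

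1. Delete every plus 1. Define duration as end minus start, less the sum of (restart minus stop) over all interruptions. The sum also covers repeated pauses, which the current text does not address.
2. State that the 35 to 45 minute compliance rule is applied to this duration.

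The cost is one edited formula and one added sentence. SAP Section I.B allows changes until database lock, and no data collection or primary analysis is affected. Separately, the noncompliance definitions in protocol Section 6.4 and SAP Section VIII.A must be reconciled, so that it is clear which subjects form the treatment-compliant subset.

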4.3 Justification for Dose

Study PCN-101-02 was a randomized, placebo-controlled, double-blind, single ascending dose study of the safety, tolerability, and pharmacokinetics of PCN-101 that included a relative safety comparison of PCN-101 and S-ketamine. Healthy subjects were administered a single IV infusion of PCN-101 at total doses of 5, 15, 30, 60, 100, and 150 mg or placebo over a 40-minute period. The safety and tolerability of PCN-101 at different doses and of 15 mg S-ketamine was assessed using reported AEs, changes in hematology and serum chemistry, changes in vital signs

and physical examination findings, ECG and pulse oximetry findings, sedation (as measured by the MOAA/S), and the development of dissociative or perceptual changes (as measured by the CADSS, BPRS, and 5D-ASC).

The study evaluated 58 healthy subjects. Forty-eight (48) subjects were randomized to 6 dose levels of PCN-101 (N=36) or placebo (N=12) in the single-ascending dose portion of the study. Ten additional subjects were evaluated in a parallel and cross-over relative safety comparison of 150 mg PCN-101 (N=10) and 15 mg S-ketamine (N=10).

The primary objective was to identify an acceptable tolerated dose of PCN-101 and compare this dose to the safety profile of 15 mg S-ketamine. Dose ranging using single ascending doses of PCN-101-02 demonstrated that doses of $PCN-101 \leq 150$ mg had acceptable safety profiles as single IV infusions.

Both 30 mg and 60 mg doses of PCN-101 resulted in fewer transient elevations in mean systemic blood pressure, less sedation, fewer psychological or psychotic and dissociative effects, and fewer episodes of altered consciousness than 100 mg or 150 mg doses of PCN-101.

Based on the results of study PCN-101-02, 30 mg and 60 mg of PCN-101 were selected to be evaluated in this proof-of-concept study.

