9.4.3 Safety Analyses

All safety analyses will be performed on the Safety Analysis Set.

Adverse Events

Adverse events will be coded using the Medical Dictionary for Regulatory Activities (MedDRA; Version 23.0 or higher). Treatment-emergent adverse events (TEAEs) are AEs with onset or worsening after the start of study treatment. The AE summaries will be primarily based on TEAEs. The number and percentage of subjects with TEAEs will be summarized by treatment group, system organ class, and preferred term for all TEAEs, treatment-related TEAEs, SAEs, serious TEAEs, severe TEAEs, TEAEs of special interest, and all TEAEs leading to study drug discontinuation. All TEAEs will be further summarized by maximum severity and causality. The TEAEs of special interest will be identified in the SAP.

All AEs will be presented in a by-subject listing. Serious AEs, severe AEs, and AEs leading to study discontinuation or death will be presented in separate listings.

Clinical Laboratory Tests

Laboratory data will be summarized using descriptive statistics for each parameter, including change from baseline at each assessment time by treatment group. Frequency tables or shift tables will be used to present the number and percentage of subjects with laboratory values within/outside reference ranges. All laboratory data will be present in the listings. A by-subject listing will also be provided for subjects with abnormal laboratory results.

Electrocardiogram

Descriptive statistics will be used to summarize the observed and change from baseline values of the following ECG parameters at each assessment time by treatment group: heart rate, PR interval, QRS interval, QT interval, and QTcF. All ECG data will be present in listings.

Vital Signs

Vital sign parameters including temperature, pulse/heart rate, respiratory rate, SpO₂, and blood pressure will be summarized descriptively for both the observed and change from baseline values at each assessment time by treatment group. Frequency tabulations will be provided for abnormalities as applicable.

Other Safety Questionnaires and Assessments

All physical examination results will be listed by subject.

Prior and concomitant therapies will be summarized separately and tabulated for each treatment group using frequencies and percentages. Percentages will be based on the number of subjects in each treatment group. Prior and concomitant medications will be listed by subject.

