The tables will display counts and percentages of subjects who reported at least one TEAE in each system organ class represented in the AE data. Within each system organ class, the tables will display the counts and percentages of subjects reporting at least one TEAE, as designated by the preferred terms.

If a subject has multiple occurrences of an adverse event, the worst severity grade and the highest level of relationship to study drug for a given AE will be used in summary tables.

Adverse events that have missing onset dates will be considered as treatment emergent unless the stop date is known to be prior to the first administration of the study medication. If the adverse event onset date is partial, the date will be correlated as far as possible with the date of study medication. Adverse events will be assumed to be treatment-emergent, unless there is clear evidence (through comparison of partial dates) to suggest that the adverse event started prior to the

first dose of study medication. Detailed imputation rules for dates can be found in [Section V.C.2 Partial Dates](#).

An overall summary of AE table will summarize the number of subjects who meet the following criteria for:

1. Number of subjects with any AEs
2. Number of subjects with any TEAEs
3. Number of subjects with any TEAEs by maximum severity
4. Number of subjects with any Treatment-emergent SAEs
5. Number of subjects with any Treatment-emergent SAEs by maximum severity
6. Number of subjects with any TEAEs related to study drug (possibly, probably, definitely related or unknown)
7. Number of subjects with any SAEs related to study drug (possibly, probably, definitely related or unknown)
8. Number of subjects with any TEAEs resulting in death
9. Number of subjects with any severe TEAEs related to study drug (possibly, probably, definitely related or unknown)
10. Number of subjects with any TEAEs resulting in the permanent discontinuation of study treatment
11. Number of subjects with any treatment-emergent SAEs resulting in the permanent discontinuation of study treatment
12. Number of subjects with any TEAEs resulting in the discontinuation from study
13. Number of subjects with any TEAEs of COVID-19

Treatment-emergent AEs will be tabulated according to the MedDRA system organ class and preferred term and will include the following categories. Analysis marked with and asterisk (*) will also be tabulated based on the preferred term in descending frequency only.

1. All TEAEs *

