For chemistry, hematology, and urinalysis, any laboratory abnormalities will be listed separately. The abnormal laboratory listing will provide the entire profile for each subject and parameter with an abnormal post-baseline result.

E. Vital Signs and Pulse Oximetry

For vital signs (systolic and diastolic blood pressure, tympanic/temporal temperature, pulse, respiratory rate) and pulse oximetry, summaries of actual values and changes from baseline will be presented by treatment group for each scheduled assessment timepoint, beginning with the Baseline visit. For this analysis, any lab collection performed on unscheduled analysis visits will not be summarized, with the exception of the inclusion of unscheduled pre-dose assessments used in the classification of baseline, as described in [Section V.B Definition of Baseline](#).

Vital signs will consist of three (3) blood pressure measurements (recorded at intervals of at least 1 minute). The arithmetic mean of the three (3) blood pressure readings will be recorded in the CRF and used for this analysis.

Temperature data collected via tympanic or temporal methods will be pooled for analysis.

The incidence of clinically relevant abnormality will be summarized by treatment. For this analysis, any unscheduled post-baseline records will be included for assessment. A listing of clinically relevant abnormality vital signs will be displayed.

Table 4 Potential Clinically Relevant Abnormalities in Vital Signs

Parameter	Unit	Low	High
Systolic blood pressure	mmHg	≤ 90 or CFB ≤ -20	≥ 180 or CFB ≥ 20
Diastolic blood pressure	mmHg	≤ 50 or CFB ≤ -15	≥ 105 or CFB ≥ 15
Pulse	beats/min	≤ 50 or CFB ≤ -15	≥ 120 or CFB ≥ 15
Temperature	°C	CFB ≤ -2	≥ 38.3 or CFB ≥ 1.1
Respiratory Rate	breaths/min	<8	Not applicable
Oxygen Saturation	%	< 90%	Not applicable

CFB = change from Baseline.

All vital signs data will be listed

F. Physical Examination

All physical examination results will be listed by subject.

G. Electrocardiograms

12-Lead ECGs will be obtained using an ECG machine that automatically calculates the parameters for analysis. If abnormal, the ECG needs to be repeated.

An overall interpretation of the ECG results, PR intervals, RR intervals, QT uncorrected intervals, QT intervals corrected by Fridericia's formula (QTcF) will be listed by subject.

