Subjects are counted only once in each therapeutic class category. Prior and concomitant medications will be summarized separately and tabulated for each treatment group using frequencies and percentages. Percentages will be based on the number of subjects in each treatment group. Prior and concomitant medications and therapies will be listed by subject.

I. Assessments of Alertness/Sedations and other Safety Rating Scales

For the following rating scales, summaries of actual values (total scores) and changes from baseline will be presented by treatment group for each scheduled assessment timepoint, beginning with the Baseline visit.

A listing displaying the scores for these scales (individual items and total) will be provided by subject.

- Modified Observer's Assessment of Alertness/Sedation (MOAA/S)
- Clinician-Administered Dissociative States Scale (CADSS)
- Brief Psychiatric Rating Scale - Modified 4 Components (BPRS+)

The 5-Dimensional Altered States of Consciousness Rating Scale (5D-ASC) is only assessed post-baseline and for only one (1) time during the study. A listing displaying the details of the 5D-ASC will be provided by subject.

J. Others

Any other assessments which were not described in any previous sections will be listed based on the FAS. This includes (and not limited to) the following:

- Non-compliance in inclusion or exclusion criteria
- Massachusetts General Hospital Antidepressant Response Questionnaire (MGH-ATRQ)
- Mini-International Neuropsychiatric Interview (MINI)

IX. Interim Analysis

No interim analysis is planned.

X. References

XI. Appendices

A. Missing or Partial Date Imputation

For records with missing AE onset/resolution date, the following procedure will be employed for use in determining whether the AE is treatment emergent:

- AE onset dates with missing day and non-missing month will be assumed to occur on the first day of the non-missing month, except for AEs occurring in the month and year of first dosing, in which case the date will be imputed using the date of first dosing.

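### The SAP neither identifies the TEAEs of special interest nor plans the by-arm table that the protocol promises, so related adverse event terms have no prespecified per-subject count

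*SAP*

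**What the plan says.** Protocol 9.4.3, under Adverse Events, lists the TEAE categories to be summarised by treatment group, system organ class and preferred term. The list includes "serious TEAEs, severe TEAEs, TEAEs of special interest, and all TEAEs leading to study drug discontinuation". It then says: "The TEAEs of special interest will be identified in the SAP". The synopsis makes the same commitment.

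SAP VIII.B begins its table list with "Treatment-emergent AEs will be tabulated according to the MedDRA system organ class and preferred term and will include the following categories" and gives eight categories: all, related, serious, serious related, severe, severe related, leading to permanent discontinuation of treatment, and by maximum severity. A separate overall summary has 13 rows, and there are five listings. Special-interest events appear in none of these. One row names a specific event: "Number of subjects with any TEAEs of COVID-19".

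Protocol 4.3 says that 30 mg and 60 mg produced "fewer transient elevations in mean systemic blood pressure, less sedation, fewer psychological or psychotic and dissociative effects, and fewer episodes of altered consciousness" than the two highest Phase 1 doses.

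For the safety scales MOAA/S, CADSS and BPRS+, SAP VIII.I plans that "summaries of actual values (total scores) and changes from baseline will be presented by treatment group for each scheduled assessment timepoint". For vital signs and oxygen saturation, SAP VIII.E adds: "The incidence of clinically relevant abnormality will be summarized by treatment". The 5D-ASC receives only a by-subject listing in SAP VIII.I, whereas Protocol 9.4.3 names it among the scales to be summarised by treatment group.

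**The concern.** The protocol hands the definition of special-interest events to the SAP, and the SAP does not supply it. A programmer who follows the SAP will not produce the promised table, and the SAP text does not explain the omission.

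Safety and tolerability of two doses against placebo is a stated objective, and the development rationale rests on fewer dissociative and psychotomimetic effects. Such effects can be reported in different words from one subject to the next. If they are coded to different preferred terms, each row of the table is small. The number of subjects with any event of that kind is then shown nowhere, and a reader cannot rebuild it from the table. A grouping fixed in advance gives that number. A grouping chosen once the arms are known is open to the criticism that it was picked to suit the result.

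**Working it through.** The plan gives no figure on this point, so there is none to reproduce. The check is a comparison of text, followed by a small calculation that shows what a preferred-term table can and cannot tell the reader.

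**1. Promise against delivery**

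| Item | Protocol 9.4.3 | SAP |
|---|---|---|
| Special-interest TEAEs identified | Deferred to the SAP | Not done |
| By-arm table of them | Yes | Absent from 13 summary rows, 8 tables and 5 listings |
| MOAA/S, CADSS, BPRS+ by arm | Yes | Yes (VIII.I) |
| Blood pressure and oxygen saturation by arm | Yes | Yes, with incidence of threshold abnormalities (VIII.E, Table 4) |
| 5D-ASC by arm | Yes | Listing only (VIII.I) |

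**2. What the remaining summaries cover**

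Under Protocol 8.2.7 and 8.2.8, CADSS and BPRS+ are rated predose, at 40 minutes, and at 2 and 4 hours. Under 8.2.6, MOAA/S ends at 6 hours. Under 8.3.1, adverse events are collected until Day 15. An effect that arises between ratings, or after Day 1, can therefore reach the report only as an adverse event. The scale summaries give scores and changes. They do not give the number of subjects affected, the severity grade or the relation to treatment. Blood pressure is better covered, because Table 4 yields a per-subject incidence and vital signs continue to Day 15.

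**3. Why the group count cannot be recovered from the table**

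If k related terms occur in a1, ..., ak subjects of an arm of n, the number with at least one of them lies between max(ai) and min(n, sum of ai). The arm size is n = 31 (Protocol 9.2). Assume four terms with 4 subjects each. The group count is then anywhere from 4 of 31 (13%) to 16 of 31 (52%). The system organ class row counts each subject once, but it also takes in every other event of that class. It misses related terms coded to another class.

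**4. Effect of grouping, as an assumed range**

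No test on adverse events is planned, so these figures show only how visible a difference would be. They are not trial power. All rates are assumed. The grouped rate for independent terms is 1 - (1 - p)^k. The last column is the exact probability that Fisher's test gives p ≤ 0.05 with 31 per arm.

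| Assumption (active vs placebo, per term) | Grouped rates | Probability |
|---|---|---|
| One term, 12% vs 1% (equals four terms with full overlap) | 12% vs 1% | 0.12 |
| Two independent terms, 12% vs 1% | 22.6% vs 2.0% | 0.55 |
| Four independent terms, 12% vs 1% | 1 - 0.88^4 = 40.0% vs 1 - 0.99^4 = 3.9% | 0.94 |
| Four independent terms, 6% vs 1% | 21.9% vs 3.9% | 0.39 |
| Four independent terms, 12% vs 5% | 40.0% vs 18.5% | 0.37 |

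At 12% vs 1% per term, the value of grouping runs from nothing with full overlap (0.12) to large with four independent terms (0.94).

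**The case against.** The strongest reply is that the effects in question are measured directly. Protocol 4.3 shows that Phase 1 assessed sedation by MOAA/S and dissociative or perceptual change by CADSS, BPRS and 5D-ASC, with vital signs alongside adverse events. Most of these are summarised by arm here. A reader might infer from the missing table that the effects behind the choice of doses are never compared between arms. The documents do not support that. The gap concerns adverse event reports, and among the scales only 5D-ASC.

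Three other stronger readings also fail.

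- A reader might take the missing table as the test of the claim that the drug causes less dissociation. That claim is made against S-ketamine, and this trial has no S-ketamine arm. Protocol 4.3 compares 30 and 60 mg with 100 and 150 mg, not with each other or with placebo.
- A reader might conclude that any grouping must come after unblinding. SAP I.B allows changes until database lock, so this can still be avoided.
- A reader might treat the 0.94 above as power lost. It is one favourable assumed case for a test that nobody plans.

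It is also fair to say that the protocol never states which events are of special interest. The groups proposed below are inferred from the effects it names. How the terms spread over system organ classes depends on MedDRA content that the documents do not give. Recording the omission as a change from the protocol would also remove the contradiction, though it would not restore the information.

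What stands after this is narrow: a promised definition and table are missing, and no other planned output gives adverse event counts per subject for each effect.

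**Conclusion.** The point holds as a mismatch between protocol and SAP. The SAP identifies no TEAEs of special interest and plans no table of them. Adverse events related to dissociation, psychotomimetic effects, sedation, altered consciousness and blood pressure rise will be shown by arm only as separate preferred terms and broad system organ classes. The COVID-19 row does not fill the gap, since it is not labelled as special interest and is unrelated to the drug's named effects.

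The 5D-ASC listing is a second, smaller departure of the same kind. It leaves altered consciousness as the one effect named in Protocol 4.3 without its by-arm scale summary.

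The weight is minor to moderate. The safety analysis is descriptive, the study is a proof of concept, and the primary efficacy analysis is unaffected. The mismatch itself rests on the text alone. How much a grouped count would add rests on assumptions about overlap and event rates that the documents do not supply.

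**What to change.** Before unblinding, amend SAP VIII.B as follows.

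- Have the medical team agree, while blinded, a list of preferred terms for each effect the protocol names: dissociation, psychotomimetic effects, sedation, altered consciousness and blood pressure rise. Cognitive impairment is named in the study rationale but not in Protocol 4.3, so the team should decide whether to include it and record the decision.
- Add one table on the Safety Analysis Set giving the number and percentage of subjects with at least one event in each group, by arm and by maximum severity.
- Add the matching rows to the overall adverse event summary.

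In SAP VIII.I, restore the by-arm descriptive summary of 5D-ASC scores. Change from baseline cannot be given, because the scale is completed once, after dosing.

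If the sponsor decides against a special-interest table, the SAP should state this as a change from Protocol 9.4.3 and give the reason.

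The cost is SAP wording, a blinded term list, one adverse event table and one scale summary. No new data are needed. The only real burden is that the medical team must agree the terms before treatment codes are released.
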